To assess changes of mtDNA genetic features (mutations by next generation sequencing and copy numbers) in the bronchial and nasal epithelium of randomized smokers, arms will be compared pairwise. To correct for multiple comparisons, we will assume a significance threshold corresponding to one expected false discovery per 100 tests ( $p=0.01$ ). Biomarkers will be examined for comparisons between pre and post in each visit for bronchial and nasal samples separately. Generalized linear models (Poisson [mutation] and Gaussian [CN]) will be employed with feature as the dependent variable, a covariable for baseline measure, and a main effect of Arm. For CN, with 21 samples per group, considering a significance threshold of 0.01, a two-sided, two-sample t-test achieves 80% power to detect an 1.4 fold difference between arms considering a coefficient of variation of 0.32 [298]. For mutation, Poisson regression achieves 80% power to detect a mutation rate ratio of 2.7 between arms considering a significance threshold of 0.01 and 21 samples per group [299].

To investigate if changes in mtDNA alterations are associated with lung inflammation and changes in other omics features, generalized linear models (Gaussian) will be employed, with follow-up inflammatory markers and gene expression as the dependent variables, covariables for baseline levels and arm, and changes of mtDNA features ( $\Delta\text{mtDNA} = \text{Follow} - \text{Baseline}$ ) as the independent variables. Because of the number of genes that will be tested, for power we will consider a significance threshold corresponding to one expected false discovery per 10,000 tests ( $p=0.0001$ ). With 84 samples, considering a significance threshold of  $p=0.0001$  and unit standard deviations for dependent variable residuals and  $\Delta\text{mtDNA}$  features, linear regression achieves 80% power to detect a slope of 0.48.

$\text{Follow\_Expression} = \text{Baseline\_expression} + \text{arm} + \Delta\text{mtDNA feature} + e.$

Significant effects of mtDNA feature will indicate that changes gene expression (or inflammatory markers) are associated with changes in mtDNA feature while accounting for between arm effects.

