- 2) Descriptive statistics and clustering (e.g., principal components analysis [PCA]), will be performed for all biomarker data measured at the different visits. Baseline data (1st bronchoscopy) will then be compared between the four groups (3 conditions and control) using a one-way analysis of variance (ANOVA). The non-parametric Kruskal-Wallis test (continuous or ordinal variables) or the chi-square test (categorical variables) will be applied when the normality assumption of the data is not met. We will compare controls to complete substitution with the SREC (with and without nicotine) or NRT. Generalized linear models (GLM) will be employed with measurement (cell count, gene expression, etc.) as the dependent variable, a covariable for baseline measure, and a main effect of arm. Other relevant variables that are associated with the biomarker results, e.g., baseline smoking, Fagerstrom Test for Nicotine Dependence (FTND), or gender will also be included in our models as they are potential confounders. We also will assess batch effects and include batch as a co-variable in the model (all samples will be analyzed at the same time, except for cell counts). We plan to use baseline molecular measurement as a covariable rather than

modeling the change between baseline and follow-up because the former is more powerful [1]. Given the large dynamic range of the cell count and the 'omics data, we will initially consider a normal distribution. If the data are determined to deviate from normality, we will log-transform the data or assume a non-normal distribution of residuals (such as Poisson) for the GLM. Urine propylene glycol (PG) will be measured at the 2nd bronchoscopy visit and compared to baseline to verify e-cig use. As an exploratory analysis, urinary PG will be used as the exposure predictor variable assessing the biomarker results as dependent variables. Urine anatabine, urine anabasine and nicotelline will be used to confirm complete substitution or a predictor variable for smoking reduction. The cotinine level will be used as a surrogate for smoking reduction.

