- 4) For mtDNA features, Model 1 is also used. CN is expected to be Gaussian, while mutation rate is expected to be low counts; therefore, a t-test was powered for CN and Poisson [3] for mutation rate. Because there will only be several comparisons here, the significance threshold used for power corresponds to one expected false discovery per 100 tests. We believe that this threshold is a good balance between potential Type I and Type II errors, given the number of tests. The coefficient of variation was calculated from results in the

literature, as cited in the main body of the protocol. For CN, with 21 samples per group, considering a significance threshold of 0.01, a two-sided, two-sample t-test achieves 80% power to detect an 1.4 fold difference between arms considering a coefficient of variation of 0.32 [4]. For mutation, Poisson regression achieves 80% power to detect a mutation rate ratio of 2.7 between arms considering a significance threshold of 0.01 and 21 samples per group [5].

- 5) For associations between mtDNA and other 'omics features, we assume the regression model [6]:

$$\text{Followup_Expression} = \text{Baseline_expression} + \text{arm} + \Delta\text{mtDNA feature} + e,$$

Where $\Delta\text{mtDNA} = \text{Followup_mtDNA} - \text{Baseline_mtDNA}$. We consider this model across all arms. The effect of arm is included as a covariable to ensure that associations are not simply due to both features being associated with arm; rather, we are looking for a more direct relationship. Again, we consider a significance threshold corresponding to one expected false discovery per 10,000 tests, as described above. To generalize, we assume unit standard deviations of the dependent and independent variables (each feature will have a different standard deviation, so results are calculated in terms of standard deviations). With 84 samples, considering a significance threshold of $p=0.0001$ and unit standard deviations for dependent variable residuals and ΔmtDNA features, linear regression achieves 80% power to detect a slope of 0.48.

- 6) For comparing mtDNA features between nasal and bronchial samples, mixed Poisson or mixed Gaussian will be employed with a random effect for subject, and a main effect for location (bronch vs. nasal):

$$\text{Feature} = \text{sample\&rand} + \text{location} + e.$$

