Poisson regression achieves at least 80% power to detect a mutation rate ratio of 2.1 between the sample origins considering a significance threshold of 0.01 and 84 paired samples. For mtDNA CN, a two-sided paired t-test achieves 80% power to detect a mean of paired differences of 0.4 standard deviations of the paired differences considering 84 paired samples and a significance threshold of 0.01. Correlations (CN) and Cohen's kappa (mutational burden) will also be calculated between the two tissues for each of the assays.

- 7) As a secondary aim, we will test if treatment is associated with differences in mtDNA genetic features between tissues. Generalized linear mixed models will be employed with measurement (mtDNA genetic features) as the dependent variable, a random effect for patient, covariables for baseline measure and sample origin, a main effect of arm, and an interaction effect of origin* arm:

$$\text{Feature} = \text{sample\&rand} + \text{baseline} + \text{origin} + \text{arm} + \text{arm*origin} + e.$$

This analysis will investigate whether treatment is associated with differences between tissues. The interaction term will be comprised of four groups of 21 for each pair of arms.

To conservatively estimate the power to detect this interaction effect, the power will be calculated while adjusting the significance threshold for the number of pairwise tests ($n=6$; $p=0.01/6=0.0017$). A two-sided, two-sample t-test achieves 80% power to detect an 1.5 fold difference between any two groups considering a significance threshold of 0.0017, 21 samples per group, and a coefficient of variation of 0.32 [4].

- 8) As an additional exploratory analysis, we will study dose-response associations of cigarette smoking with biomarkers at baseline bronchial and nasal samples separately. Generalized linear models (again, Poisson or Gaussian) will be fit with biomarkers as the dependent variable and covariables (e.g., cigarettes per day [cigs/day] and urinary cotinine levels, separately), adjusting for confounders, such as sex and age. THC use will also be examined.

References

1. Zhang, S., et al., *Empirical comparison of four baseline covariate adjustment methods in analysis of continuous outcomes in randomized controlled trials*. Clin Epidemiol, 2014. **6**: p. 227-35.
2. Julious, S.A., *Sample sizes for clinical trials with normal data*. Stat Med, 2004. **23**(12): p. 1921-86.

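### The between-arm mutation comparison is analysed and powered as plain Poisson with no allowance for residual overdispersion, and Poisson is left open as a fallback for cell counts

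*SAP*

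**What the plan says.** SAP item 4 applies Model 1 of item 3 (follow-up value on baseline value and arm) to the mtDNA features. It expects low mutation counts and says that "a t-test was powered for CN and Poisson [3] for mutation rate". Protocol section 4.g.ii agrees: "Generalized linear models (Poisson [mutation] and Gaussian [CN]) will be employed with feature as the dependent variable", with baseline and arm as the other terms. On the test level, item 4 says that "the significance threshold used for power corresponds to one expected false discovery per 100 tests". Its power claim, for 21 samples per group, is: "For mutation, Poisson regression achieves 80% power to detect a mutation rate ratio of 2.7 between arms considering a significance threshold of 0.01".

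Neither document gives a base mutation rate, a dispersion parameter or the sidedness of the Poisson test. Item 3 lists the power inputs as CVs, p-values and effect sizes.

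Item 6 states that "Poisson regression achieves at least 80% power to detect a mutation rate ratio of 2.1 between the sample origins" with 84 pairs, but its analysis model has a random subject effect. Item 7 has a random patient effect. Item 8 uses Poisson or Gaussian GLMs without one.

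For measurements that explicitly include cell counts, SAP item 2 and protocol section 4.g.i start from normality. If that fails, they offer either a log transform or to "assume a non-normal distribution of residuals (such as Poisson) for the GLM". Item 3 also plans to check the model assumptions afterwards for features found to be associated, and names no action if the check fails.

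**The concern.** A Poisson GLM with one count per subject forces the residual variance to equal the mean. Subjects here are 21 to 52 years old and smoke from 5 cigarettes a day upwards, so their underlying mutation rates may well differ. A baseline count of about one mutation carries little information on a subject's own rate, and the follow-up bronchial sample comes from the opposite lung. The baseline covariate can therefore absorb only part of that variation. What is left makes the Poisson standard errors too small.

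At stake are the 1% error rate of the pairwise arm tests and the 80% power claim. For cell counts, which are among the primary outcomes, a Poisson error model would ignore almost all of the biological variation.

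**Working it through.** **Inputs from the documents.** Alpha 0.01, rate ratio (RR) 2.7, 21 per arm (42 per pairwise comparison), 80% power: SAP item 4. RR 2.1 with 84 pairs: item 6. Smokers' cell count mean 2.41E+07, SD 1.48E+07, and planning CV 0.26: protocol 4.g.ii.

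**Assumptions.** Two-sided test; base rate λ mutations per sample; gamma-distributed subject rates with squared CV k. The documents give no value for λ or k.

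**The plan's own figures.** Poisson-regression sample-size formula for a binary covariate, equal groups:

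N = [2·z(0.995) + z(0.80)·√(2 + 2/RR)]² / (λ·(ln RR)²), with z = 2.576 and 0.842.

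- RR 2.7: [5.152 + 0.842 × 1.656]² = 42.84; (ln 2.7)² = 0.9866; N = 43.4/λ. Setting N = 42 gives λ = 1.03.
- RR 2.1: [5.152 + 0.842 × 1.718]² = 43.53; (ln 2.1)² = 0.5505; N = 79.1/λ. Setting N = 84 gives λ = 0.94.
- With λ = 1.0 the detectable ratios are 2.74 (N = 42) and 2.06 (N = 84), which round to the stated 2.7 and 2.1.

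One unstated base rate near 1.0 thus reproduces both figures. A two-sample Wald formula on the log rate ratio would instead need λ = 0.77 for 80% power at 2.7.

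**Error rate of the planned model.** Gamma-Poisson counts at baseline and follow-up, 21 v 21, no arm effect, λ = 1.03. Poisson GLM on log(baseline + 1) and arm, nominal 0.01, 20,000 runs per row:

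| Squared CV of subject rates | Plain Poisson | Dispersion-scaled |
|---|---|---|
| none | 0.7% | 0.7% |
| 0.25, persistent | 1.5% | 0.8% |
| 0.5, persistent | 1.9% | 0.7% |
| 1, persistent | 3.0% | 0.8% |
| 0.25 persistent + 0.25 per visit | 2.7% | 0.7% |
| 0.5 persistent + 0.5 per visit | 6.5% | 0.7% |

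A repeat gave 1.6 to 2.9% for the persistent rows and 2.7 to 6.7% for the last two. At λ = 3, the three persistent rows become 3.0, 3.8 and 4.7%.

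**Power of a valid test.** Negative binomial Wald test: Var(ln RR) = (1/λ + 1/(2.7λ) + 2k)/21; power = Φ(ln 2.7/SE − 2.576). For λ = 1.034 and k = 0.25: (0.967 + 0.358 + 0.5)/21 = 0.0869; SE = 0.295; 0.993/0.295 − 2.576 = 0.79; Φ(0.79) = 0.79.

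| k | Power, λ = 1.03 | RR at 80% power, λ = 1.03 | n per arm for RR 2.7, λ = 1.03 | Power, λ = 0.77 |
|---|---|---|---|---|
| 0 | 0.92 | 2.39 | 16 | 0.80 |
| 0.1 | 0.87 | 2.53 | 19 | 0.75 |
| 0.25 | 0.79 | 2.74 | 22 | 0.67 |
| 0.5 | 0.66 | 3.08 | 28 | 0.56 |
| 1 | 0.47 | 3.81 | 40 | 0.41 |

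The λ = 1.03 column starts at 0.92, not 0.80, because the Wald formula is less conservative than the formula used above to find λ.

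**Cell counts.** Variance/mean = (1.48E+07)²/2.41E+07 ≈ 9.1 million, so the SD is √9.1 million ≈ 3,000 times the Poisson SD. An unadjusted Poisson test at 0.01 with no true difference rejects whenever |Z| > 2.576/3,000 ≈ 0.00086, about 99.9% of the time. With CV 0.26 it is 99.8%. The smallest significant relative difference is 2.576 × √(2/(21 × 2.41E+07)) ≈ 0.00016, or about 0.02%.

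**The case against.** Several stronger readings are tempting, and the documents do not support them.

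- A reader might infer that every mutation analysis is plain Poisson. Items 6 and 7 carry a subject or patient random effect, and item 7 is powered by a t-test.
- A reader might infer that rate ratios 2.7 and 2.1 contradict each other. That follows only if the 84 pairs enter the formula as 168 samples, which gives about 1.7. Entered as N = 84, the two figures agree.
- A reader might compute the error rate without the baseline covariate and get 2.0, 3.5 and 6.5% for k = 0.25, 0.5 and 1 at a base rate of 1.0. The planned model adjusts for baseline, and item 2 also allows covariates such as baseline smoking, FTND and gender. The condition for trouble is variation left after adjustment, not merely that subjects differ.
- A reader might infer that any heterogeneity destroys the 80% power. At base rate 1.03 and k = 0.1 a valid test still has 87%.
- A reader might infer that cell counts will be analysed as Poisson. Item 2 offers it as one example beside the log transform, and item 3 treats cell counts as Gaussian for power.

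It is also fair that base rate and dispersion are assumed here, that the plan's silence on dispersion does not prove that none was considered, and that item 3 has an assumption check. That check is written for 'omics features, applies only after a positive result and has no stated consequence, so it does not protect the test level. What remains is the between-arm model in item 4, the same gap in item 8, and the permitted Poisson option for cell counts.

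**Conclusion.** The concern holds for item 4 (with protocol 4.g.ii), item 8 and the cell-count fallback. In item 4, residual variation in subject rates makes the 0.01 test too liberal: about 1.5 to 3% with persistent variation only (k = 0.25 to 1), and about 2.7 to 6.7% with equal visit-specific variation added (0.25 to 0.5 each), at an assumed base rate of about 1 per sample. Dispersion scaling held the level at or below about 1.1% in every case run.

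The stated power is plausible but cannot be verified, because the base rate is missing. At base rate 1.03, a valid test falls just below 80% at k = 0.25 and further beyond it; at 0.77 it is below 80% with any overdispersion.

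The cell-count part rests on the protocol's own mean and SD. If the Poisson option were used, almost any arm difference would be significant. Enrolment is not affected, since the sample size is argued from cell counts treated as Gaussian.

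**What to change.** - In SAP item 4 (and the matching text in protocol 4.g.ii) and item 8, use negative binomial or quasi-Poisson models for mutation counts, with dispersion-scaled or robust standard errors.
- In SAP item 2 and protocol 4.g.i, delete Poisson as an option for cell counts; keep the log transform, or allow a family with free dispersion.
- State the base mutation rate and the dispersion assumed for item 4, and restate the detectable rate ratio over a range of k. At base rate 1.03 it runs from 2.39 (k = 0) to 3.81 (k = 1).
- Leave the models in items 6 and 7 as they are.

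The cost is a wording change and one extra parameter per model. The stated detectable ratio may become less favourable. No new data and no change to trial conduct are needed.

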After 10 weeks of their assigned condition (+/- 3 days), subjects will undergo a second bronchoscopy as described above. Subjects assigned to the nicotine-SREC or placebo-SREC conditions will undergo inhalation assessment. In an effort to standardize the timing and recent product exposure, subjects be instructed to use the device immediately prior to the visit. Subjects who report the device was not used as instructed will be asked to use the device before proceeding with the visit. Subjects assigned to the nicotine-SREC condition will also undergo a nicotine boost assessment that includes two blood draws, one prior to and one after a timed use session.

Subjects assigned to the control condition (smoking their usual brand) will undergo all the procedures as the other conditions, except the nicotine boost and inhalation assessment. The specific value using controls to users, rather than only assessing within subject changes for pre- to post-bronchoscopy biomarkers, is our ability to evaluate the impact of being enrolled in a smoking study, e.g., smokers in the control group might reduce their exposures because they are enrolled in a smoking study.

A biorepository of the lung samples, saliva, urine, blood, nasal lavage and nasal brushings will be established. A Data and Safety Monitoring Board will be established as described below.

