**The Effects of a Standardized Research E-Cigarette on the Human Lung:
A Clinical Trial with Bronchoscopic Biomarkers**

NCT03691350

Statistical Analysis Plan, 09/19/22

SREC SAP

The Specific Aim for this two year project is:

To assess inflammatory changes over 10 weeks (8 weeks experimental condition) for lung and urine biomarkers in smokers in a clinical trial where smokers are randomized to: continued use (n=32), complete switching to the nicotine standardized research electronic cigarette (SREC) (n=32), complete switching to the placebo SREC (n=32), or complete switching to nicotine replacement therapy (NRT) (n=32).

- 1) We will enroll 128 subjects (32 per group). For power calculations, we will use a conservatively planned 66% retention rate at 5 weeks, knowing that we have a 100% retention for never smokers receiving serial bronchoscopies. Thus, the final sample size will be 21 subjects per group (n=84). Although we expect a higher retention rate, we assume 66% to ensure that we have the minimal numbers required to reach meaningful conclusions. Since follow-up samples would not be obtained from subjects that do not finish the treatment protocol, and these samples (inflammation/omics) are our primary outcomes, we cannot use an 'intent to treat' strategy since dropouts will have missing outcome data for any analyses including follow-up measurements (the primary Aim). In light of this, we will compare dropout rates between arms and with demographic/clinical to ensure that the analyses results are not biased by unbalanced dropouts. We will also test for differences in baseline molecular measurements between subjects that dropout after baseline samples are taken vs. subjects that complete the protocol. While we will make every effort to minimize the missing data for this study, missing data can arise due to various reasons. Violation of missing completely at random (MCAR) will be checked by evaluating whether any covariates are associated with missing data. If so, these covariates will be subsequently included and controlled for in the GL(M)M models. In addition, sensitivity analyses will also be conducted using results from multiple imputation.

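### The mtDNA–expression model adjusts for arm but not for smoke exposure within arms, so a significant slope is an arm-adjusted association and not evidence of a more direct link

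*SAP*

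**What the plan says.** SAP item 5 models follow-up expression as baseline expression plus arm plus the change in an mtDNA feature. On pooling it says "We consider this model across all arms". It gives the reason for the arm term as "The effect of arm is included as a covariable to ensure that associations are not simply due to both features being associated with arm", and continues: "rather, we are looking for a more direct relationship". The planned sample is 84 subjects, 21 per arm.

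Protocol section 4.g.ii has the same model, with inflammatory markers also named as outcomes. Its reading of a significant result is softer: the outcomes "are associated with changes in mtDNA feature while accounting for between arm effects".

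On exposure within arms, Protocol section 4.a.iii explains the value of controls partly because "smokers in the control group might reduce their exposures because they are enrolled in a smoking study". SAP item 2 says: "Urine anatabine, urine anabasine and nicotelline will be used to confirm complete substitution or a predictor variable for smoking reduction". Partial switching is therefore foreseen.

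On the effect of exposure, the Background (Protocol section 3) reports graded expression changes with urine cotinine at low smoking levels. It also treats mtDNA alterations as a possible indicator of tobacco toxicity.

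Protocol Table 3 schedules the urine tobacco-use panel, including nicotelline, anatabine, total NNAL and PAHs, at both bronchoscopies. None of these markers is a term in item 5.

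**The concern.** An arm term removes the part of a shared cause that differs on average between arms. The likely shared cause here is how much smoke each person was still inhaling, and that differs between people in the same arm. Someone who kept smoking more than others in the arm could differ from them in both the mtDNA change and follow-up expression. The regression would then show a slope even if mtDNA and expression had no link of their own.

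What is at stake is interpretation. The analysis asks whether mtDNA change goes with inflammation and gene expression beyond both responding to treatment. As specified, it cannot separate that from two independent responses to the same cigarettes, although the markers that would help are already to be measured.

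**Working it through.** **The plan's own figure.** Item 5 states 80% power for a slope of 0.48 with n = 84 and alpha = 0.0001. With unit SDs for outcome and predictor, the slope is a correlation. Taking the test as two-sided, the Fisher approximation gives (3.891 + 0.842)/√81 = 0.526, and tanh(0.526) = 0.482. A noncentral-t calculation gives 0.476. The figure reproduces on that convention. Item 5 also mentions unit SD for the residuals; on that convention the detectable slope would be 0.541. This side point does not affect what follows.

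**Can exposure act as a within-arm shared cause?** The documents support each step: controls may cut down (Protocol 4.a.iii), switchers may only reduce (SAP item 2), and smoking affects expression and mtDNA (Protocol section 3). They give no sizes.

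**Assumed inputs (none from the documents).** E is the fractional reduction in exposure.
- Controls: mean 0.10, SD 0.15.
- Switchers: E = 1 with probability q; otherwise uniform on 0.2–0.9 (mean 0.55, variance 0.49/12 = 0.0408).
- mtDNA change = aE + noise; follow-up expression = aE + 0.5 × baseline + independent noise. There is no direct link.
- R is the share of each feature's variance explained by E over all arms, leaving out the baseline part of expression.

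**Exposure variance left within arms, q = 0.5.**
- Switcher mean = 0.5 + 0.5 × 0.55 = 0.775.
- Switcher variance = 0.5 + 0.5 × (0.3025 + 0.0408) − 0.775² = 0.0710.
- Within arms = 0.25 × 0.0225 + 0.75 × 0.0710 = 0.0589.
- Between arms = 0.25 × 0.75 × (0.775 − 0.10)² = 0.0854.
- Within-arm fraction f = 0.0589/0.1443 = 0.41.

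The same steps give f = 0.26 for q = 0.75 and 0.14 for q = 0.90.

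**Slope left after arm and baseline.** Let k = f × R/(1 − R). The partial correlation between the two features is r = k/(1 + k). With four covariate terms (three for arm, one for baseline), the test statistic is centred near √77 × atanh(r).

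For q = 0.5 and R = 0.3: k = 0.408 × 0.4286 = 0.175, so r = 0.149 and the centre is 8.775 × 0.150 = 1.32. The chance of passing 1.96 in either direction is about 0.26.

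| Full quitters | R | r | Rejection at 0.05, formula | Simulation (20,000 trials) |
|---|---|---|---|---|
| 50% | 10% | 0.043 | 6.7% | 6.4% |
| 50% | 20% | 0.093 | 12.9% | 12.8% |
| 50% | 30% | 0.149 | 26.0% | 26.7% |
| 75% | 10% | 0.029 | 5.7% | 5.9% |
| 75% | 20% | 0.062 | 8.5% | 8.5% |
| 75% | 30% | 0.102 | 14.6% | 14.9% |
| 90% | 10% | 0.015 | 5.2% | 5.2% |
| 90% | 20% | 0.034 | 6.0% | 6.2% |
| 90% | 30% | 0.057 | 7.9% | 7.9% |

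The top of this range is not a bound. In the 50%/30% case exposure correlates about √0.149 = 0.39 with each feature within arms. A within-arm correlation of 0.5 gives r = 0.25 and about 63% rejection at 0.05.

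**Adding an exposure marker (50%, 30%).** With exposure known exactly, rejection returns to 5.1%. With a marker of reliability 0.8 over the whole sample, it falls to about 8–9%, not to 5%. Within arms that marker is weaker: its error variance is 0.25 × 0.1443 = 0.0361, so its within-arm reliability is 0.0589/(0.0589 + 0.0361) = 0.62.

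**The case against.** The text is narrower than a quick reading suggests. A reader might infer that the plan says arm adjustment guarantees a direct relationship, or that smoking-driven slopes will be reported as direct. It does not. The SAP says the arm term guards against links due to arm, which is true. Directness is stated as an aim, and only as a comparison. The protocol claims no more than an association after accounting for arm. In the simulations the two features really are associated given arm and baseline, so a rejection answers the protocol's question correctly; it is an error only for a claim of directness. This stands, and it sets the form of the point.

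A reader might also infer that the 0.0001 error rate is broken. In the 50%/30% case, rejection at that level is about 0.0048, again only as an error about directness. But 0.0001 is a power-planning threshold; SAP item 3 says FDR will be used in practice. The inflated-threshold reading is not supported.

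The plan also pushes toward abstinence: a bonus for daily home CO at or below 6 ppm on at least 5 days a week, possible removal by the PI for non-compliance, and no follow-up samples from those who do not finish. These may reduce within-arm variation. They do not make verified abstinence a condition of analysis, and removal is tied to product return and use reports.

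Finally, the printed equation may be schematic, since item 2 adds other relevant variables and batch to the arm comparisons. The variables it names as potential confounders are baseline smoking, FTND and gender, not on-study exposure, and item 5 does not refer back. Item 8's smoking dose-response analysis uses baseline samples only. The gap remains.

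**Conclusion.** The point holds as a limit on interpretation. Item 5 delivers an arm-adjusted association. It cannot by itself support a more direct mtDNA–expression relationship, because smoke exposure can vary within arms and act on both sides.

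The size is not known. Under the assumed values, rejection at 0.05 with no direct link is about 5–8% when exposure explains 10% of each feature's variance or 90% of switchers quit fully. It rises to about 26% with 50% full quitters and 30% explained. Everything rests on the assumed quit rates, the spread of reduction and the strength of the exposure effects.

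The randomised arm comparisons, which serve the Specific Aim, do not depend on this model. Nor would a slope that survives marker adjustment prove directness: marker error leaves residual confounding, and smoke need not be the only shared cause (THC use and batch are others).

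**What to change.** In SAP item 5 and the matching paragraph of Protocol section 4.g.ii:

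1. Fit the model as written and again with the change from first to second bronchoscopy in a smoke marker that supplied nicotine does not drive. Candidates in the planned urine panel are nicotelline, anatabine, total NNAL and PAH metabolites. Name one in advance. Cotinine is unsuitable, because the nicotine-SREC and NRT arms take in nicotine without smoke.
2. Report the mtDNA slope and its interval with and without the marker.
3. Replace the clause "rather, we are looking for a more direct relationship" with a description of the result as an arm-adjusted association, or an arm- and smoke-exposure-adjusted association for the second model. State that marker error leaves residual confounding.

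The assays are already scheduled at both visits. The cost is one degree of freedom and a wider interval for the mtDNA slope where the marker tracks the mtDNA change. Before any gain from a smaller residual variance, the standard error grows by 1/√(1 − ρ²), where ρ is their within-arm correlation: about 8% at ρ = 0.39, 15% at 0.5 and 40% at 0.7.
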